6.3.1.2. Between group assessment

Exploratory comparisons between each investigational RSV vaccine group and (minus) the control group (*placebo*), and between the RSV vaccine groups will be done in terms of the percentage of subjects reporting any \geq Grade 2, Grade 3 AE (solicited and unsolicited), and/or any fever $> 38.5^{\circ}\text{C}$, and/or any vaccine-related SAE during the 7-day follow-up period after vaccination.

- PreF-30 *minus* placebo
- PreF-60 *minus* placebo
- PreF-120 *minus* placebo

- PreF-120 minus PreF-30
- PreF-120 minus PreF-60
- PreF-60 minus PreF-30

The standardised asymptotic 95% CI for the difference between the investigational RSV vaccine groups as well as between the investigational RSV groups and (minus) the control group will be computed.

6.4. Analysis for ranking RSV formulations

The totality of data and sum total of evidence for particular dose(s) in terms of safety and immunogenicity will be evaluated by study team in addition to the analyses described in section 6.1 and 6.3 on formulation selection. The desirability index approach described in the section below will be used as a descriptive tool to guide the formulation selection. In addition, any pertinent information from outside this study will be evaluated and may be used by the study team to help to make the final decision on a dose/formulation.

6.4.1. Definition of desirability in the context of Simulations

A desirability approach will be based on safety/reactogenicity and immunogenicity data up to 1 month post-vaccination.

This method is a multi-criteria decision making approach based on desirability functions. The main idea is to identify for each endpoint a desirability function that associates any value to another one between 0 and 1 depending on its desirability ('0' being considered as not desirable at all and '1' as the most desirable). An index with values between 0 and 1 will be created for each endpoint. An overall desirability index can be calculated by computing a weighted geometric mean of the endpoint indexes. By definition, this overall index also takes values between 0 and 1 and characterises the level of desirability of any candidate formulation by a single value [Dewé, 2015].

The desirability index calculations will include reactogenicity and safety data up to Day 7 post vaccination (on the TVC) and immunogenicity data at 30 days post-vaccination (on the ATP cohort for immunogenicity up to Day 30). The formulations will be ranked based on the values obtained with this overall desirability index.

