The following group and sub-group names will be used for the statistical analyses:

Group order in tables	Group label in tables	Group definition for footnote
1	30 PreF	30 µg PreF
2	60 PreF	60 µg PreF
3	120 PreF	120 µg PreF
4	Control	Placebo

Some tables might be presented by age category according to the following description:

Sub-group	Sub-group order in tables	Sub-group label in tables	Sub-group definition for footnote
Age	1	18-32Y	18-32 years old subjects
	2	33-45Y	33-45 years old subjects

- **Blinding:** Observer-blind in Epoch 001 and single-blind in Epoch 002.

Table 3 Blinding of study epochs

Study Epochs	Blinding
Epoch 001	observer-blind
Epoch 002	single-blind

- **Sampling schedule:**
 - **Blood samples for haematology/biochemistry** will be collected (~10 mL) from all subjects at Visit 1 (Day 0), Visit 2 (Day 7), Visit 3 (Day 30), Visit 4 (Day 60) and Visit 5 (Day 90).
 - **Blood samples for humoral immune response evaluation** will be collected (~17 mL) from all subjects at Visit 1 (Day 0), Visit 3 (Day 30), Visit 4 (Day 60) and at Visit 5 (Day 90).
 - **Nasal swabs** will be collected from subjects in case of a medically attended respiratory tract infection from enrolment (Visit 1) until study end (Contact 3).
- **Type of study:** self-contained
- **Data collection:** Electronic Case Report Form (eCRF).
- **Safety monitoring:**
 - When the first 25% of subjects (i.e. ~100 subjects; ~25 subjects per study group) have been vaccinated, enrolment will be paused until completion of an unblinded review by a GSK internal Safety Review Committee (iSRC). Continuation of study enrolment will be conditional to a favourable outcome of the iSRC evaluation of all available safety and reactogenicity data collected up to at least 7 days post-vaccination (including Day 7 haematology and biochemistry parameters). In addition, the blinded safety data will be reviewed by GSK Biologicals' Safety Review Team (SRT) on a regular basis throughout the study. Analyses related to iSRC evaluation will be described in a separate document (SAP/TFL for iSRC).

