3. OBJECTIVES

3.1. Primary Objective

- To rank different formulations of the investigational RSV vaccine based on safety/reactogenicity and immunogenicity data up to 1 month post-vaccination (Day 30).

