13. ANNEX 3 CALCULATION OF INDIVIDUAL AND OVERALL DESIRABILITY INDEX

The section below provide the details on how to calculate individual desirability index and overall desirability index score based on Annex E in the Protocol.

Reactogenicity

A logistic regression model will be fitted on each reactogenicity endpoint (any Grade 2/3 general AE and any related SAE, Grade 2/3 fever) reported during the 7-day follow-up period after vaccination, including all RSV formulations.

- The vaccine group as the fixed effect
- The age groups (18-32 years and 33-45 years) as the categorical covariant if deemed necessary.

The estimation of indication rate will be tabulated by treatment group. The SAS codes can be used as reference:

[figure not shown]
```
proc logistic data=React;
  class Treatment AgeGroup / param=glm;
  model response (event='AE')= Treatment| AgeGroup;
  lsmeans Treatment / ILINK e diff oddsratio adjust=bon cl;
run;
```

For any Grade 2/3 general AEs and any related SAEs, the incidence rate estimate (IR) will be transformed in a [0,1] desirability index using the following function:

$$DR1 = \begin{cases} \frac{1}{1 + \exp(-50 * (0.25 - IR))}, & \text{if } IR \leq 0.25 \\ \frac{1}{1 + \exp(-25 * (0.25 - IR))}, & \text{if } IR \geq 0.25 \end{cases}$$

where IR is the incidence rate estimated by the model. This function will allocate a desirability value of 1, 0.5 and 0 to incidence rate equal to 0.1, 0.25 and 0.5 respectively (see Figure 2). But the calculation equally weights Grade 2/3 general AEs and any related SAEs.

Figure 2 Desirability function for the incidence rate of Grade 2/3 general AEs and related SAEs - for each investigational RSV vaccine formulation

[figure not shown]

For Grade 2/3 fever, the incidence rate estimate (IR) will be transformed in a [0,1] desirability index using the following function:

$$DR2 = \frac{1}{1 + \exp(-120 * (0.05 - IR))}$$

where IR is the incidence rate estimated by the model. As illustrated in Figure 3, the function will allocate desirability values of 1, 0.5 and 0 to incidence rate equal to 0, 0.05 and 0.1 respectively.

Figure 3 Desirability function for the incidence rate of Grade 2/3 fever - for each investigational RSV vaccine formulation

Finally, the reactogenicity index will be computed by taking the geometric mean of the 2 indexes:

$$DR = \sqrt{DR1 * DR2}$$

Immunogenicity

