The ANCOVA model will be fitted on the log-transformed titre for each immune response of neutralising anti-RSV-A and PCA separately including

- The vaccine group as the fixed effect
- The pre-vaccination titre/concentration and age groups (18-32 years and 33-45 years) as the covariates if deemed necessary

The mean estimations of GMTs/GMCs for each treatment group at Day 30 and its 95% CI will be provided for immunogenicity desirability calculation. The estimated GMT and LL will be tabulated by treatment group.

As formulations inducing a high immune response will be considered suitable, the lower limit (LL) of the estimated GMT/C adjusted for pre-vaccination titres will be the statistical criterion considered for decision making.

[figure not shown]
Neutralising anti-RSV-A titres

The LL of the GMT estimate will be transformed into a [0, 1] desirability index using the function:

$$DI1 = \frac{1}{1 + \exp(1.5 * (9.5 - LL))}$$

where LL is the lower limit of the 95% confidence interval of the GMT adjusted for pre-vaccination titres in log base 2. The function was chosen to have a desirability of 0 at LL value ≤ 6 log2 (=128), and a desirability of 1 at LL value ≥ 13 log2. This function is illustrated in [Figure 4](#).

Figure 4 Desirability function for neutralising anti-RSV-A GMTs - for each investigational RSV vaccine formulation

[figure not shown]
PCA concentrations

The LL of the GMC adjusted for pre-vaccination titres estimate will be transformed using the following function:

$$DI2 = \begin{cases} \frac{1}{1 + \exp(0.05 * (150 - LL))}, & \text{if } LL \leq 150 \\ \frac{1}{1 + \exp(0.025 * (150 - LL))}, & \text{if } LL \geq 150 \end{cases}$$

As illustrated in [Figure 5](#), a PCA response of 25, 150 and 400 µg/mL will have a desirability value of 0, 0.5 and 1 respectively.

Figure 5 Desirability function for PCA concentrations - for each investigational RSV vaccine formulation

Finally, the immunogenicity index will be computed by taking the geometric mean of the 2 indexes:

$$DI = \sqrt{DI1 * DI2}$$

Overall desirability index

The overall desirability index for each formulation will be obtained by computing the following weighted geometric mean: $D = DR^{0.4} * DI^{0.6}$.

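### The primary ranking orders single values of the desirability index D, and no interval or ranking probability is planned for D or for the rank

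*SAP*

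**What the plan says.** The references are to SAP Amendment 4 (01-Jun-2018).

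- Section 3.1 makes ranking the formulations on data up to Day 30 the primary objective.
- Section 6.4.1 gives the only ranking rule: "The formulations will be ranked based on the values obtained with this overall desirability index".
- Annex 3 builds the index: "The overall desirability index for each formulation will be obtained by computing the following weighted geometric mean", D = DR^0.4 × DI^0.6, where DR = √(DR1 × DR2) and DI = √(DI1 × DI2).
- DR1 (Grade 2/3 general AE or related SAE) and DR2 (Grade 2/3 fever) take the model-estimated rate. DI1 (RSV-A neutralising titre) and DI2 (PCA) take the lower 95% limit of the adjusted GMT or GMC.
- Templates 57 and 58 show DR1, DR2, DR, DI1, DI2, DI and D as single values per group.
- Section 6.4 sets the status of the index: it "will be used as a descriptive tool to guide the formulation selection", beside the totality of the data. Section 7 calls all comparative analyses descriptive and asks for caution.
- The planned size is about 100 per group (section 2, Table 1). This agrees with the safety pause: "When the first 25% of subjects (i.e. ~100 subjects; ~25 subjects per study group) have been vaccinated".

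**The concern.** The order of the three D values is the answer to the primary objective. Each D is a function of four estimates from about 100 subjects, yet nothing in section 6.4, Annex 3 or the mock tables says how far D would move in another sample. Section 6.4.1 mentions simulations in its title but specifies none. Because D is continuous in the antibody limits, three formulations always come out in a strict order, even if they are identical. A team guided by D then cannot tell from the planned output whether a gap of, say, 0.10 reflects the formulations or the sample.

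**Working it through.** **1. The plan's own anchors.** For DR1, "This function will allocate a desirability value of 1, 0.5 and 0 to incidence rate equal to 0.1, 0.25 and 0.5 respectively". The function returns 0.9994, 0.500 and 0.0019. For fever, "the function will allocate desirability values of 1, 0.5 and 0 to incidence rate equal to 0, 0.05 and 0.1 respectively". DR2 returns 0.9975, 0.500 and 0.0025. DI1 returns 0.0052 at 6 log2 and 0.9948 at 13 log2. DI2 returns 0.0019, 0.500 and 0.998 at 25, 150 and 400 µg/mL. The functions therefore behave as described. (The gloss of 6 log2 as 128 is a separate slip, since 2^6 = 64.)

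**2. How much each component moves D.** Written out, D = (DR1 × DR2)^0.2 × (DI1 × DI2)^0.3.

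- 3, 4, 5 and 6 fevers in 100 give DR2 = 0.92, 0.77, 0.50 and 0.23. Going from 5 to 6 multiplies D by (0.231/0.500)^0.2 = 0.857. Going from 2 to 3 multiplies it by only 0.988.
- At a true AE rate of 0.25 the standard error is √(0.25 × 0.75/100) = 0.043, and DR1 runs from 0.90 to 0.25 over ±1 SE. At an observed 20%, one more AE per 100 multiplies D by only 0.990.

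**3. One worked point.** The assumptions, none of them in the SAP, are: n = 100, AE 20%, fever 2%, RSV-A mean 10 log2 with SD 1.2, PCA GMC 120 with SD 0.6 on the natural log scale.

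- LL for RSV-A: 10 − 1.96 × 1.2/10 = 9.765, so DI1 = 0.598.
- LL for PCA: 120 × exp(−1.96 × 0.6/10) = 106.7, so DI2 = 0.103.
- DR1 = 0.924 and DR2 = 0.973.
- D = (0.924 × 0.973)^0.2 × (0.598 × 0.103)^0.3 ≈ 0.42.

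First-order contribution of each component to the SD of ln D (exponent × slope of the log index × standard error):

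| Component | Calculation | SD of ln D |
|---|---|---|
| PCA | 0.3 × 0.05 × (1 − 0.103) × (106.7 × 0.06) | 0.086 |
| AE, 20% | 0.2 × 50 × (1 − 0.924) × 0.040 | 0.030 |
| RSV-A | 0.3 × 1.5 × (1 − 0.598) × 0.12 | 0.022 |
| Fever, 2% | 0.2 × 120 × (1 − 0.973) × 0.014 | 0.009 |
| Fever, if 5% | 0.2 × 120 × (1 − 0.500) × 0.0218 | 0.262 |

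At 2% fever PCA dominates; at 5% fever dominates.

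**4. Three identical formulations, simulated (best minus worst D).** Rows 1 to 3 use the SDs of step 3 and independent endpoints. Rows 4 to 6 use other assumptions: fever nested in the AE endpoint, assays correlated 0.6, RSV-A SD 1.0 log2, PCA SD 0.25 on log10. Observed proportions stand in for model estimates throughout.

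| Row | AE | Fever | RSV-A (log2) | PCA (µg/mL) | Median | Upper tail |
|---|---|---|---|---|---|---|
| 1 | 15% | 1% | 11 | 250 | 0.028 | 90th percentile 0.060 |
| 2 | 20% | 2% | 10 | 120 | 0.073 | 90th percentile 0.140 |
| 3 | 20% | 5% | 10 | 120 | 0.142 | 90th percentile 0.266 |
| 4 | 10% | 0.5% | 11 | 250 | 0.025 | at least 0.1 in 0.1% |
| 5 | 25% | 2% | 11 | 250 | 0.163 | at least 0.1 in 77% |
| 6 | 30% | 4% | 11 | 250 | 0.251 | at least 0.1 in 89% |

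Ties had probability 0.000 to three decimals. In row 2, removing all reactogenicity noise leaves a median of 0.060, and removing all immunogenicity noise leaves 0.036.

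**5. A real difference.** With AE 20/22/24%, fever 2/3/4%, RSV-A 9.8/10/10.2 and PCA 110/125/140, the true D values are about 0.36, 0.43 and 0.48. The formulation with the highest true D ranks first in 63% of simulated trials.

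**The case against.** The plan is not silent on uncertainty, and several points stand.

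- DI1 and DI2, with 60% of the weight, use lower confidence limits, so imprecision already lowers D. True, but a limit also varies from sample to sample. It penalises imprecision without saying how uncertain D is.
- Section 6.2.1.2 plans GMT and GMC ratios between the formulations with 95% CIs and Tukey adjustment. Section 6.3.1.1 plans exact CIs for AE percentages. These help a careful reader but do not combine into an interval for D.
- Section 6.3.1.2 plans CIs for reactogenicity differences. That composite covers any AE of Grade 2 or above, not only general AEs, pooled with fever and related SAEs, so it is neither the DR1 nor the DR2 endpoint. Section 9 (Amendment 3 changes) removes the table from the final analysis. The removal is stated for the final analysis only, and the Day 30 analysis may still carry it.
- The index is descriptive and one input among several. This limits the consequence of a chance ranking. It does not explain why other descriptive estimates in the SAP carry intervals and this one does not.

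A reader might infer that identical formulations would routinely be reported as clearly ranked. The documents do not support this: the SAP never calls a rank clear, and the gaps are small on the plateaus. Nor is D as a whole very steep. DR1 and DR2 are steep, but the exponent of 0.2 damps them away from their midpoints, and in row 2 most of the spread comes from the immune components.

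**Conclusion.** The point holds in limited form. The primary objective is answered by ordering single values of D, and no interval or ranking probability is planned for D or the rank. The median chance gap between identical formulations is about 0.03 on the plateaus, 0.07 in a middle case and about 0.14 to 0.25 near the midpoints. The noise comes from both the immunogenicity side, chiefly PCA, and the reactogenicity side. All these sizes rest on rates, titres and SDs that the SAP does not give, so they show a range and predict nothing for this trial. Because the index is descriptive, this is an inexpensive improvement to how the primary objective is reported; it does not invalidate the index.

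**What to change.** Add to section 6.4.1 and Template 58 a bootstrap (for example 5,000 resamples) of subjects within formulation and age stratum. Keep each subject's endpoints together, so that fever nested within general AEs and the correlation between assays are preserved. In each resample, refit the planned models and recompute IR, LL, DR, DI and D. State beforehand how the fever rate is obtained when a resample has no fever in a formulation, because the logistic model then has no finite estimate.

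Report descriptively:

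- the 95% percentile interval of D for each formulation;
- intervals for the three pairwise differences in D;
- the probability that each formulation ranks first.

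Do not attach a rule that a rank counts only if an interval excludes 0. That would put an unadjusted significance test into a plan that is deliberately descriptive.

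The index, its weights and the data collected stay as they are. The cost is programming time, and the report may have to say that the formulations are not distinguishable on D.

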6.4.2. Derived endpoints

The following endpoints will be computed and taken into account in the desirability analysis:

1. Incidence rate of any Grade 2 and any Grade 3 general AE (solicited and unsolicited) and any vaccine-related SAE during the 7-day follow-up period after vaccination for each investigational RSV vaccine formulation.
2. Incidence rate of Grade 2 and Grade 3 fever during the 7-day follow-up period after vaccination for each investigational RSV vaccine formulation.

3. Geometric mean of neutralising antibody titres against RSV-A at Day 30 adjusted for pre-vaccination titres.
4. Geometric mean of PCA concentrations at Day 30 adjusted for pre-vaccination titres.

Each individual desirability index will be calculated based on data and tabulated by the treatment group and endpoints above. The details on how to calculate individual desirability index in terms of reactogenicity and immunogenicity and overall desirability index are elaborated in Annex 2.

6.5. Analysis of medically attended RTIs

The analysis will be performed on the ES by study group.

The proportion of subjects (with 95% CI) with at least one medically attended RTI (all causes) will be calculated by group.

Viral load assessed by the quantitative PCR (RSV-A/B) of RSV-RTI cases will be listed for any cases where this assay is performed.

Medically attended RSV-associated RTI co-infected or colonisation with another viral etiology identified by multiplex PCR will be described.

Medically attended RTI with any viral etiology identified by multiplex PCR will be described.

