2. STUDY DESIGN

Figure 1. Study design overview

V = Visit; D = Day; VACC = vaccination; BS = blood sample; h/b = blood sample for haematology/biochemistry; Imm = blood sample for immunogenicity; C = contact; RSV = Respiratory Syncytial Virus; PCR = Polymerase Chain Reaction.

1 Safety data up to (minimum) 7 days post-vaccination (including Day 7 haematology and biochemistry parameters) of the first 25% of subjects vaccinated in the study will be reviewed by iSRC.

2 In case of a MA-RTI (e.g. visit to the GP for respiratory symptoms including but not limited to cough, sputum production, difficulty breathing), the subject will be asked to contact the Investigator to enable completion of an event related eCRF and the collection of a nasal swab within 72h after the medical attendance.

Vertical lines stand for analysis on all subjects.

- **Experimental design:** Phase II, observer-blind, randomised, controlled, multi-country, study with four parallel groups.
 - **Duration of the study:** the intended duration of the study will be approximately 1 year from Visit 1 to study conclusion (Day 360).
 - Epoch 001: Primary starting at Visit 1 (Day 0) and ending at Visit 5 (Day 90).
 - Epoch 002: Follow-up phase starting one day after Day 90 and ending at Day 360 contact.
- **Primary Completion Date (PCD):** Visit 3 (Day 30).
- **End of Study (EoS):** Last testing results released of samples collected at Visit 5 (i.e. last testing results released for the assays related to the primary and secondary endpoints).
- **Study groups:**

Table 1 Study groups and epochs foreseen in the study

Study groups	Number of subjects	Age (Min/Max)	Epochs	
			Epoch 001	Epoch 002
30 PreF	~100	18 - 45 years	x	x
60 PreF	~100	18 - 45 years	x	x
120 PreF	~100	18 - 45 years	x	x
Control	~100	18 - 45 years	x	x

Table 2 Study groups and treatment foreseen in the study

Treatment name	Vaccine/ Product name	Study Groups			
		30 PreF	60 PreF	120 PreF	Control
30 µg PreF	PreF-30 ----- NaCl	X			
60 µg PreF	PreF-60 ----- NaCl		X		
120 µg PreF	PreF-120 ----- NaCl			X	
Placebo	Formulation buffer S9b				X

- **Control:** Placebo control
- **Vaccination schedule:** One intramuscular vaccination at Day 0.
- **Treatment allocation:** Subjects will be randomised using a centralised randomisation system on internet (SBIR) at Day 0. The randomisation algorithm will use a minimisation procedure accounting for age (18 - 32 years or 33 - 45 years) and centre.

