3.2. Secondary objectives

- To evaluate the reactogenicity and safety of a single intramuscular dose of the RSV investigational vaccines up to study conclusion.
- To evaluate the immunogenicity of a single intramuscular dose of the RSV investigational vaccines up to 90 days after vaccination (Day 90).
- To further assess the safety of the investigational RSV vaccines by evaluating whether a single dose of the vaccines induces antibodies against the residual host cell protein neogenin (NEO) up to 1 month post-vaccination (Day 30).
- To estimate the incidence of medically attended RSV-associated RTIs up to study conclusion.

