5.1.1. Exposed Set (ES)

The ES will include all subjects with study vaccine administration documented:

- A **safety** analysis based on the ES will include all vaccinated subjects
- An **immunogenicity** analysis based on the ES will include all vaccinated subjects for whom immunogenicity data are available.

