9. CHANGES FROM PLANNED ANALYSES

In order to align to ICH and CDISC terminology the Total Vaccinated Cohort and the According To Protocol cohort have been renamed Exposed Set (ES) and Per-Protocol Set (PPS) respectively.

Changes in Amendment 1 mainly include the following.

For the sequence of analysis, the IDMC evaluation was newly added to review all available safety and reactogenicity data (including Day 30 haematology and biochemistry parameters) of all enrolled subjects up to at least 30 days post administration of the study vaccine or placebo.

Since the document of criteria for eliminating subjects from analysis will not be used anymore, the table of Elimination codes has been modified for more clarity. Attribution of code 1070 to a subject requires CRDL confirmation. Attribution of these elimcodes including 1040, 2040, 2050, 2060, 2070 and 2120 to subject need CRDL review of individual data listings.

In the analysis of immunogenicity section, the distribution of fold increase of the antibody titres against RSV-A and RSV-B and concentrations against NEO have been added.

For the analysis of safety, the percentage of subjects reporting each individual solicited local AE (any, each grade, resulting in medically attended visit) during the 7-day follow-up period after vaccination will also be tabulated based on maximum intensity per subject for each study vaccine group; the percentage of subjects reporting each individual solicited general AE (any, each grade, any related, any Grade 2 related, any Grade 3 related, resulting in medically attended visit) during the 7-day follow-up period after vaccination will also be based on maximum intensity per subject for each study vaccine group.

Evaluation of last secondary objective 'To estimate the incidence of medically attended RSV-associated RTIs up to study conclusion' will be performed based on MA-RTIs rather than MA-RSV associated RTIs.

The cut-off for the updated (qualified) version of the PCA assay will be set at the level of the assay LLOQ (9.60 µg/mL). Hence the SAP does not need to define handling of data between the LOD and LLOQ anymore, as results will only be provided as of the LLOQ. It only needs to be defined that for results below the cut-off (LLOQ), an arbitrary value of half of the cut-off will be considered for calculation of GMC and fold increase.

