11.2.5. Safety

- For a given subject and the analysis of solicited symptoms within 7 days post-vaccination, missing or non-evaluable measurements will not be replaced. Therefore the analysis of the solicited symptoms based on the Total Vaccinated Cohort will include only vaccinated subjects for doses with documented safety data (i.e., symptom screen completed). More specifically the following rules will be used:
 - Subjects who documented the absence of a solicited symptom after one dose will be considered not having that symptom after that dose.
 - Subjects who documented the presence of a solicited symptom and fully or partially recorded daily measurement over the solicited period will be included in the summaries at that dose and classified according to their maximum observed daily recording over the solicited period.
 - Subjects who documented the presence of a solicited symptom after one dose without having recorded any daily measurement will be assigned to the lowest intensity category at that dose (i.e., 37.5°C for fever or grade 1 for other symptoms).
 - Doses without symptom sheets documented will be excluded.
- For analysis of unsolicited adverse events, such as serious adverse events or adverse events by primary MedDRA term, and for the analysis of concomitant medications, all vaccinated subjects will be considered. Subjects who did not report the event or the concomitant medication will be considered as subjects without the event or the concomitant medication respectively.
- The preferred route for recording temperature in this study will be oral. For the analysis, temperatures will be coded as follows:

Grade	Temperature for oral, axillary or tympanic route	Temperature for rectal route
0	< 37.5°C	< 38.0°C
1	≥ 37.5°C - ≤ 38.5°C	≥ 38.0°C - ≤ 39.0°C
2	> 38.5°C - ≤ 39.5°C	> 39.0°C - ≤ 40.0°C
3	> 39.5°C	> 40.0°C

Note that for all tables described in this section, the way the percentage of subjects will be derived will depend on the event analysed (see table below for details). As a result, the N value will differ from one table to another.

Event	N used for deriving % per subject for Vaccination phase
Concomitant vaccination	All subjects with study vaccine administered
Solicited general symptom	All subjects with at least one solicited general symptom documented as either present or absent (i.e., symptom screen completed)

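### MA-RTI incidence to study conclusion is a crude proportion of all vaccinated women, so early withdrawals who are event-free pull it slightly low; a censored Day 360 estimate would remove this cheaply

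*SAP*

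**What the plan says.** References are to SAP Amendment 4 unless stated.

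The objective in Section 3.2 is "To estimate the incidence of medically attended RSV-associated RTIs up to study conclusion". Section 2 puts study conclusion at Day 360, about one year after vaccination. Section 9 records that the evaluation of this objective "will be performed based on MA-RTIs rather than MA-RSV associated RTIs", so the event analysed is MA-RTI of any cause.

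Section 6.5 sets the population, "The analysis will be performed on the ES by study group", and the estimator, "The proportion of subjects (with 95% CI) with at least one medically attended RTI (all causes) will be calculated by group". On the population, Section 5.1.1 says: "The ES will include all subjects with study vaccine administration documented". There is no follow-up requirement.

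Section 6.5 has no person-time, censoring rule, completer denominator or sensitivity analysis. Incomplete follow-up is foreseen elsewhere: Section 5.3 lists short follow-up as a reportable deviation, and Section 6.1.1 tabulates withdrawals by reason. Neither feeds into the MA-RTI estimate.

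Section 11.2.5 has a rule for unsolicited adverse events and concomitant medication: "Subjects who did not report the event or the concomitant medication will be considered as subjects without the event or the concomitant medication respectively". Section 6.5 does not cite it.

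**The concern.** Incidence up to study conclusion is a quantity with a fixed horizon of about 12 months. A simple n/N estimates it without bias only if everyone is observed to that horizon or has had the event first. A woman who leaves on Day 40 with no MA-RTI contributes 40 days of observation but is counted as if she had been observed, event-free, for 360. Swab collection depends on the subject contacting the investigator (Section 2), so an infection after withdrawal is unlikely to be recorded.

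The error runs in one direction and grows with the loss. Because Section 6.5 reports by group, a group that loses more women would show a slightly lower figure than another group with the same true risk. The confidence interval reflects the number of women, not how long they were followed.

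**Working it through.** The SAP states no MA-RTI rate and no dropout rate, so there is no figure to reproduce. The check gives the direction and size of the bias under stated assumptions.

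**Inputs from the SAP.** Horizon 360 days and about 100 women per group (Section 2); denominator all vaccinated women (Sections 5.1.1 and 6.5); exact Clopper-Pearson 95% CI for a within-group proportion (Section 11.1).

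**Assumptions.** True Day 360 risk *R* = 20% (10% as a variant); a fraction *d* lost by Day 360, independently of RTI risk; MA-RTIs before withdrawal counted, those after it not recorded; constant hazard λ = −ln(1 − *R*).

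**Expected crude proportion.** With *F*(*u*) the risk up to withdrawal time *u*,

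p = (1 − d)·R + d·mean of F(u)

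For losses spread uniformly over 360 days, the mean of F(u) is 1 − R/λ. With *R* = 0.20, λ = 0.2231, so the mean is 1 − 0.20/0.2231 = 0.1037.

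- *d* = 5%: 0.95 × 0.20 + 0.05 × 0.1037 = 0.1952, a relative shortfall of 2.4%.
- *d* = 10%: 0.90 × 0.20 + 0.10 × 0.1037 = 0.1904, shortfall 4.8%.
- *d* = 20%: 0.80 × 0.20 + 0.20 × 0.1037 = 0.1807, shortfall 9.6%.

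If 10% all leave at Day 90, F = 1 − exp(−0.2231 × 90/360) = 0.0543 and p = 0.18 + 0.10 × 0.0543 = 0.1854, a shortfall of 7.3%.

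**Sensitivity to the dropout pattern and the risk.** With exponential dropout, p = h/(h + g)·(1 − exp(−(h + g))), where h = λ and g = −ln(1 − d). At *R* = 20% this gives 19.5%, 19.0% and 18.0% for *d* = 5%, 10% and 20%. At *R* = 10% it gives 9.75%, 9.50% and 8.98%. The relative shortfall stays near d/2 for risks from 2% to 30%.

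**Bound.** Since F(u) lies between 0 and *R*, the relative shortfall lies between 0 and *d* whatever the shape of the hazard, provided withdrawal is independent of risk. Seasonality can move it within that range.

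**Unequal losses.** With *R* = 20% in both groups, 5% loss in one and 20% in the other, the uniform model gives 19.5% against 18.1%, a spurious gap of 1.4 percentage points (19.5% against 18.0%, or 1.5 points, with exponential dropout).

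**Scale.** The exact 95% CI for 20/100 is 12.7% to 29.2%, and for 10/100 it is 4.9% to 17.6%. For a difference between two groups of 100 at 20%, the standard error is √(2 × 0.20 × 0.80/100) = 5.7 points, a 95% half-width of about 11 points. The bias is 1.0 point at 10% loss, and the spurious gap is about 1.5 points at most in this example.

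**The case against.** The best defence is that little depends on this number. The primary ranking uses Day 7 reactogenicity and Day 30 immunogenicity (Section 6.4). Section 6.5 plans no between-group MA-RTI comparison, and Section 7 makes all comparisons descriptive. A cumulative proportion is also a legitimate reading of incidence: Section 6.4.2 uses the term incidence rate for proportions of subjects. Attrition is partly visible already, because withdrawals and short follow-up are reported by group, and Section 9 adds MA-RTI tables at 30, 60 and 90 days, where less follow-up can be lost. All of this stands and sets the weight of the point. It does not remove a one-directional error in the only estimate offered for the objective.

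Some stronger readings are tempting but not supported:

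- A reader might infer that every early withdrawal counts as event-free. Only women without an MA-RTI at withdrawal do; an earlier MA-RTI still counts.
- The 330 to 390 day interval for the conclusion contact in Template 10 might be taken as further evidence of understatement. It is symmetric around Day 360 and shows none.
- The non-reporter rule in Section 11.2.5 might be read as governing MA-RTI. It is written for unsolicited events and medication. The point does not need it, since n/N on the Exposed Set has the same effect.
- Unequal loss might be thought able to hide a respiratory safety signal. A gap of about 1.5 points against a half-width of about 11 does not support that. Respiratory safety also has other sources: the SAP for the IDMC review provides individual MA-RTI listings, and Section 6.3.1.1 describes SAEs in detail throughout the study.
- That no event can be captured after withdrawal is an assumption here. The SAP does not say so, and the protocol may address it.

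**Conclusion.** The point holds as a minor bias in a secondary, descriptive estimate. The crude proportion understates Day 360 MA-RTI risk whenever women who are event-free and still at risk leave early. That direction follows from the estimator and the denominator, given that later events go unrecorded. The size is conditional: roughly half the loss fraction in relative terms with evenly spread, non-informative losses and a constant hazard; about three quarters of it if all losses come at Day 90; and never more than the loss fraction if withdrawal is independent of risk. Group figures would be slightly distorted if losses differ. The bias is well inside the confidence interval at about 100 per group, and the formulation ranking does not use this figure.

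**What to change.** In Section 6.5, add a Kaplan-Meier cumulative incidence of first MA-RTI at Day 360 by group, with 95% CI, measured from vaccination and censored at withdrawal or last contact. Show person-time by group beside it, and keep the crude n/N as the descriptive line. Kaplan-Meier is preferable to a Poisson rate per person-year because RTIs may be seasonal and a constant rate is doubtful. It also deals with conclusion contacts that fall before or after Day 360.

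The cost is one extra table from event and last-contact dates that the study should already hold, plus a second figure to explain. It assumes non-informative withdrawal, which is milder than treating women who leave as event-free to Day 360. The change does not recover an RSV-specific incidence, because the event remains MA-RTI of any cause; that substitution is a separate matter.
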